3.2 Secondary Endpoint

The following ranked secondary endpoints will be tested in a hierarchical order, only if the null hypothesis for the primary endpoint has been rejected:

1. Achievement of PPASI 75 response at Week 16
2. Achievement of PPASI 90 response at Week 16
3. Achievement of sPGA of 0 or 1 with at least a 2-point reduction from Baseline at Week 16
4. Achievement of PPASI 100 response at Week 16

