9.0 Efficacy Analyses

9.1 General Considerations

All efficacy analyses will be conducted among the ITT Population. All statistical tests will be performed at a 2-sided alpha level of 0.05.

The Primary Analysis will be conducted after all continuing subjects complete Week 16 and all data pertaining to Period A are cleaned. This will be the only and final analysis for efficacy in Period A. Study sites and subjects will remain blinded to their initial treatment assignment for the duration of the entire study.

For categorical endpoints, comparisons will be made between risankizumab and placebo using the Cochran-Mantel-Haenszel (CMH) test, adjusting for the actual values of stratification factors (Baseline ppIGA and Baseline BSA categories). In case of any stratum with zero subject in either treatment group, no stratification factor will be controlled. Non-responder imputation (NRI) incorporating multiple imputation (MI) to handle missing data due to COVID-19 (NRI-C) will be the primary approach to handle missing values.

For continuous endpoints, comparisons will be made between risankizumab and placebo based on the fixed term of treatment from a Mixed-effect Model Repeat Measurement (MMRM) model including the Baseline value and observed measurements at all post-baseline visits, adjusting for the fixed effects of treatment, actual values of stratification factors, visit and treatment-by-visit interaction as covariates. The MMRM will be the primary approach to handle missing values.

"Baseline" refers to the last non-missing observation on or before the date of the first administration of study drug or the date of randomization if no study drug is administered. For variables where the assessment time is collected on the ePRO device, the baseline measurement must be prior to the time of the first administration of study drug.

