2.5.1 Analysis of Each Dataset

For each of the K 'complete' datasets, the CMH test will be used to estimate the treatment difference versus placebo and the corresponding standard error.

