MODEL *//*OVERRIDE MISSING VALUES NOT DUE TO COVID-19 WITH TRADITIONAL
NRI*/
DATA ALLF; SET ALL;
  /*COVID19_XX='Y' IF MISSING AT WEEK XX IS DUE TO COVID-19; IF NOT,
OVERRIDE WITH TRADITIONAL NRI*/
  /*VARIABLE PPASI75NRI_XX: TRADITIONAL NRI DATA AT WEEK XX, WHICH
COVERS THE SPECIAL HANDLING SUCH AS THE BEFORE-AND-AFTER EXCEPTION IN
THE PARTICULAR STUDY PERIOD*/
  IF COVID19_16 NE 'Y' THEN PPASI75_16= PPASI75NRI_16;
RUN;
PROC SORT DATA=ALLF; BY _IMPUTATION_ SUBJID; RUN;

/*****
/*ANALYSIS MODEL*/
/*****

```

```
/*KEY CODE: ANALYZING EACH 'COMPLETE' DATASET*/  
/*****/  
/*INDIVIDUAL-LEVEL DATA --> # OF RESPONDERS & # OF SUBJECTS, TO BE READ-  
IN TO PROC STDRADE*/  
PROC FREQ DATA=ALL;  
  BY _IMPUTATION_;  
  TABLES TRT01PN*STRATAN* PPASI75_16/LIST NOCUM NOPRINT OUT=COUNT_TABLE;  
  /*WEEK 16 RESULTS AS AN EXAMPLE*/  
RUN;  
DATA COUNT_TABLE; SET COUNT_TABLE;  
  DROP PERCENT;  
RUN;  
PROC TRANSPOSE DATA=COUNT_TABLE OUT=FREQ_TABLE PREFIX=RESP;  
ID PPASI75_16;  
BY _IMPUTATION_ TRT01PN STRATAN;  
VAR COUNT;  
RUN;  
DATA FREQ_TABLE1; SET FREQ_TABLE;  
  CASE=RESP1;  
  SIZE=SUM(RESP0, RESP1);  
  KEEP _IMPUTATION_ TRT01PN STRATAN CASE SIZE;  
RUN;  
  
/*RE-ORDER TO SET 1 (PLACEBO) AS THE REFERENCE GROUP*/  
DATA FREQ_TABLE2; SET FREQ_TABLE1;  
  IF TRT01PN=2 THEN TRT01PN=0;  
RUN;  
  
/*CALCULATE THE COMMON RISK DIFF FOR EACH COMPLETE DATASET*/  
PROC STDRADE DATA=FREQ_TABLE2  
  METHOD=MH STAT=RISK EFFECT=DIFF;  
  BY _IMPUTATION_;  
  POPULATION GROUP=TRT01PN EVENT=CASE TOTAL=SIZE;  
  STRATA STRATAN / ORDER=DATA STATS(CL=NONE) EFFECT;  
  ODS OUTPUT EFFECT=EFFECT;  
RUN;  
  
/*COMBINING RESULTS USING PROC MIANALYZE*/  
/*****/  
PROC MIANALYZE DATA=EFFECT;  
  ODS OUTPUT PARAMETERESTIMATES=RISK_DIFF_MH;  
  MODELEFFECTS RiskDiff;  
  STDERR StdErr;  
RUN;
```

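### The Appendix E sample code passes a missing event count, not 0, to PROC STDRATE when an arm has no responders in a stratum; this matters for low-rate endpoints, not for the primary result

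*SAP*

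**What the plan says.** SAP 9.2.1 makes NRI-C the primary approach for categorical endpoints and refers to Appendix E for details. Appendix E 2.5.1 says that for each completed dataset "the CMH test will be used to estimate the treatment difference versus placebo and the corresponding standard error". Appendix E 3.0 gives the code:

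- PROC FREQ counts subjects by arm, stratum and response: "TABLES TRT01PN*STRATAN* PPASI75_16/LIST NOCUM NOPRINT OUT=COUNT_TABLE".
- The counts are reshaped to one row per imputation, arm and stratum: "PROC TRANSPOSE DATA=COUNT_TABLE OUT=FREQ_TABLE PREFIX=RESP".
- The denominator is built as "SIZE=SUM(RESP0, RESP1" (closing bracket not shown); the event count is the plain assignment `CASE=RESP1`.
- Both go to PROC STDRATE through "POPULATION GROUP=TRT01PN EVENT=CASE TOTAL=SIZE", with "METHOD=MH STAT=RISK EFFECT=DIFF".

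SAP 9.1 has one rule for sparse strata: "In case of any stratum with zero subject in either treatment group, no stratification factor will be controlled". It concerns strata without subjects, not strata without responders. SAP 4.0 requires the ITT population, all randomized subjects, for every efficacy analysis. The ranked secondary endpoints in SAP 3.2 end with "Achievement of PPASI 100 response at Week 16".

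**The concern.** The code protects the denominator against a missing count but not the numerator. A cell where everyone responds is handled correctly; a cell where nobody responds is not. Zero responders is a valid result and should enter as 0 out of n.

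Without an event count in one arm there is no within-stratum difference. If the procedure skips that row, the subjects of both arms in that stratum leave an analysis defined as ITT, and whether they leave depends on the outcome. If the procedure stops instead, the printed code gives no result. The endpoints at risk are those with low placebo response: possibly PPASI 100, ppIGA 0, sPGA 0, and response endpoints at Week 4. The defect is the same whichever of the two datasets, `ALL` or `ALLF`, PROC FREQ reads.

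**Working it through.** **1. The plan's own figure.** Inputs from SAP 2.4: 84 per arm, 75% versus 45%, two-sided alpha 0.05. Pooled rate 0.60; null SE = √(2 × 0.60 × 0.40 / 84) = 0.0756; alternative SE = √((0.75 × 0.25 + 0.45 × 0.55) / 84) = 0.0720. Power = Φ((0.30 − 1.96 × 0.0756) / 0.0720) = Φ(2.11) = 0.983. This agrees with the stated power of more than 90%.

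**2. What the code does to an empty cell.** The FREQ, TRANSPOSE and data steps were emulated outside SAS on illustrative data. Responders, risankizumab versus placebo, by stratum: 10/30 v 2/30, 10/30 v 1/30, 4/12 v 0/12, 4/12 v 1/12. For placebo in stratum 3 the result is `RESP0` = 12, `RESP1` missing, `CASE` missing, `SIZE` = 12.

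The Mantel-Haenszel difference is Σw·d / Σw, with w = n₁n₀/(n₁+n₀), so w = 15, 15, 6, 6. With equal arms the variance of Σw·d is Σ[x₁(n−x₁) + x₀(n−x₀)]/(4n).

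- All strata: (4.0 + 4.5 + 2.0 + 1.5)/42 = 0.286; SE = √5.604/42 = 0.0564; z = 5.07; 168 subjects.
- Stratum 3 left out: (4.0 + 4.5 + 1.5)/36 = 0.278; SE = √4.938/36 = 0.0617; z = 4.50; 144 subjects.

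**3. How often a cell is empty.** For n placebo subjects with response rate p the chance is (1−p)ⁿ.

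- p = 0.45 (planned primary rate): n = 12 gives 0.0008, n = 5 gives 0.050, n = 3 gives 0.166.
- p = 0.05 (assumed): n = 21 gives 0.341, n = 12 gives 0.540. With four placebo cells of 21, at least one is empty with probability 1 − (1 − 0.341)⁴ = 0.81.

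**4. Effect if the stratum is left out.** Simulation of 40,000 trials per setting: 84 per arm, four strata, the same rates in every stratum, rejection at |z| > 1.96. A stratum is deleted if either arm has no responder. Assumed because the documents do not give them: severe share 20-40%, share with BSA ≥ 10% of 50-80% (the protocol sets only a floor of 50%), and all rates except the last row.

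| Placebo / risankizumab | Subjects dropped | Power, all strata | Power after deletion |
|---|---|---|---|
| 5% / 20% | 24-34% | about 88% | 50-69% |
| 10% / 30% | about 11% | about 93% | 84-86% |
| 20% / 50% | 1-4% | about 99% | less than 1 point lower |
| 30% / 60% | 0-2% | about 98% | less than 1 point lower |
| 45% / 75% (planned primary) | under 1% | about 98% | less than 1 point lower |

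At 5%/20% the mean estimate falls from 0.150 to 0.127-0.139. At the planned primary rates a stratum is lost in 0-18% of trials. The upper end comes from a smallest stratum of about 84 × 0.20 × 0.20 = 3 subjects per arm.

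**The case against.** The strongest reply is that the block is headed as sample code, is written for PPASI 75, and marks some data handling as omitted, so the production program may differ. The SAP text elsewhere plainly requires ITT, and no sentence tells anyone to exclude subjects. For PPASI 75 itself SAP 2.4 cites a placebo rate of about 50%, at which an empty cell is improbable unless a stratum is very small. This limits the importance of the point but does not answer it. The omitted steps concern only the merge of COVID-19 status, no zero-fill rule appears anywhere, and this is the only operational specification of the NRI-C analysis.

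A second reply is that STDRATE's handling of a missing event count is not described in the documents and was not run. That stands. A failed step would be noticed and repaired; a silent omission might not be. Every figure in the simulation table assumes silent omission.

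Third, the only placebo rates in the documents are 50% for PPASI 75 and 40% for PPASI 90. PPASI 100 must lie at or below PPASI 90, but how far below is unknown. That also stands, and is why the table extends to higher rates, where the loss is negligible.

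**Conclusion.** As printed, the code gives PROC STDRATE a wrong input whenever an arm-by-stratum cell has no responders, and nothing else in the SAP repairs it. That part follows from the code. The size of the consequence is conditional on STDRATE skipping the row, on the stratum sizes and on the endpoint's response rates. Under those assumptions it is serious at placebo rates of about 5-10% and negligible from 20% upward.

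Three stronger readings are tempting and are not supported:

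- **That the primary result is compromised.** At the planned rates under 1% of subjects would be dropped and power stays at about 98%.
- **That the defect favours the drug or undermines the testing hierarchy.** When placebo is the empty cell, the omission shrinks the effect, so the bias is against risankizumab; no inflation of false positives has been shown. PPASI 100 is last in the order, so no later test depends on it.
- **That strata appear and disappear across the 30 imputations and inflate the variance.** This could happen only where a cell's sole responders are imputed subjects, because under NRI-C only values missing due to COVID-19 vary between imputations. It was not tested.

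This is a programming specification to correct before it is used, mainly for low-rate endpoints.

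**What to change.** In Appendix E 3.0 replace `CASE=RESP1` with `CASE=SUM(RESP1,0)`. Before PROC STDRATE, check for every imputation that no `CASE` is missing and that `SIZE` sums to the ITT number in each arm. Both checks are needed: `SIZE` is already right when `CASE` is missing, so its total alone would not reveal this fault.

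Adding SPARSE to the TABLES statement is an alternative, but it would also create rows with `SIZE=0` for an arm with no subjects in a stratum. If it is used, apply the zero-subject rule of SAP 9.1 first, so that such rows are not passed on.

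The cost is one changed line and a short check. Results do not change when every cell has at least one responder.
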